8.2.1.1 Initial Tumor Imaging

Initial tumor imaging at Screening must be performed within 28 days prior to the date of randomization, and the site study team must confirm that the participant has measurable disease as defined by RECIST 1.1 criteria to confirm eligibility. Tumor imaging performed as part of routine clinical management is acceptable for use as screening tumor imaging if they are of diagnostic quality and performed within 42 days prior to the date of randomization.

8.2.1.2 Tumor Imaging During the Study

The first on-study imaging assessment should be performed at 9 weeks (63 days \pm 7 days) from the date of the first dose of pembrolizumab. Subsequent tumor imaging should be performed every 9 weeks (63 days \pm 7 days) or more frequently if clinically indicated. After 54 weeks (379 days \pm 7 days), participants who remain on treatment will have imaging performed every 12 weeks (84 days \pm 7 days). Imaging timing should follow calendar days and should not be adjusted for delays in cycle starts. Imaging should continue to be performed until disease progression is identified by the investigator (unless the investigator elects to continue treatment and follow iRECIST), the start of new anticancer treatment, withdrawal of consent, or death, whichever occurs first. All supplemental imaging must be submitted to the iCRO.

Objective response should be confirmed by a repeat imaging assessment. Tumor imaging to confirm PR or CR should be performed at least 4 weeks after the first indication of a response is observed. Participants will then return to regular scheduled imaging, starting with the next scheduled imaging time point. Participants who receive additional imaging for confirmation do not need to undergo the next scheduled tumor imaging if it is less than 4 weeks later; tumor imaging may resume at the subsequent scheduled imaging time point. Note: Response does not typically need to be verified in real time by the BICR.

Per iRECIST (Section 8.2.1.5), disease progression should be confirmed by the site 4 to 8 weeks after site-assessed first radiologic evidence of PD in clinically stable participants. Participants who have unconfirmed disease progression may continue on treatment at the discretion of the investigator until progression is confirmed by the site provided they have met the conditions detailed in Section 8.2.1.5. Participants who receive confirmatory imaging do not need to undergo the next scheduled tumor imaging if it is less than 4 weeks later; tumor imaging may resume at the subsequent scheduled imaging time point, if clinically stable. Participants who have confirmed disease progression by iRECIST, as assessed by the site, will discontinue study intervention. Exceptions are detailed in Section 8.2.1.5.

8.2.1.3 End-of-Treatment and Follow-up Tumor Imaging

For participants who discontinue study intervention, tumor imaging should be performed at the time of treatment discontinuation (± 4 week window). If previous imaging was obtained within 4 weeks prior to the date of discontinuation, then imaging at treatment discontinuation is not mandatory. For participants who discontinue study intervention due to documented disease progression, this is the final required tumor imaging if the investigator elects not to implement iRECIST.

For participants who discontinue study intervention without documented disease progression, every effort should be made to continue monitoring disease status by tumor imaging using the same imaging schedule used while on treatment calculated from the date of first pembrolizumab administration (see Section 8.2.1.2) until the start of a new anticancer treatment, disease progression, pregnancy, death, withdrawal of consent, or the end of the study, whichever occurs first.

8.2.1.4 RECIST 1.1 Assessment of Disease

RECIST 1.1 will be used by BICR as the primary measure for assessment of tumor response, date of disease progression, and as a basis for all protocol guidelines related to disease status (eg, discontinuation of study intervention). Although RECIST 1.1 references a maximum of 5 target lesions in total and 2 per organ, this protocol allows a maximum of 10 target lesions in total and 5 per organ, if clinically relevant to enable a broader sampling of tumor burden.

8.2.1.5 iRECIST Assessment of Disease

iRECIST is based on RECIST 1.1, but adapted to account for the unique tumor response seen with immunotherapeutic drugs. iRECIST will be used by the investigator to assess tumor response and progression, and make treatment decisions. When clinically stable, participants

should not be discontinued until progression is confirmed by the investigator, working with local radiology, according to the rules outlined in Appendix 8. This allowance to continue treatment despite initial radiologic PD takes into account the observation that some participants can have a transient tumor flare in the first few months after the start of immunotherapy, and then experience subsequent disease response. This data will be captured in the clinical database.

Clinical stability is defined as the following:

- Absence of symptoms and signs indicating clinically significant progression of disease
- No decline in ECOG performance status
- No requirements for intensified management, including increased analgesia, radiation, or other palliative care

Any participant deemed clinically unstable should be discontinued from study intervention at site-assessed first radiologic evidence of PD, and is not required to have repeat tumor imaging for confirmation of PD by iRECIST.

If the investigator decides to continue treatment, the participant may continue to receive study intervention and the tumor assessment should be repeated 4 to 8 weeks later to confirm PD by iRECIST, per investigator assessment. Images should continue to be sent in to the iCRO for potential retrospective BICR.

If repeat imaging does not confirm PD per iRECIST, as assessed by the investigator, and the participant continues to be clinically stable, study intervention may continue and follow the regular imaging schedule. If PD is confirmed, participants will be discontinued from study intervention.

If a participant has confirmed radiographic progression (iCPD) as defined in Appendix 8, study intervention should be discontinued; however, if the participant is achieving a clinically meaningful benefit, an exception to continue study intervention may be considered following consultation with the Sponsor. In this case, if study intervention is continued, tumor imaging should continue to be performed following the intervals as outlined in Section 8.2.1.2 and submitted to the iCRO.

[figure not shown]
A description of the adaptations and iRECIST process is provided in Appendix 8, with additional details in the iRECIST publication [Seymour, L., et al 2017]. A summary of imaging and treatment requirements after first radiologic evidence of progression is provided in [Table 11](#) and illustrated as a flowchart in [Figure 2](#).

Table 11 Imaging and Treatment After First Radiologic Evidence of Progressive Disease

	Clinically Stable		Clinically Unstable	
	Imaging	Treatment	Imaging	Treatment
First radiologic evidence of PD by RECIST 1.1 per investigator assessment	Repeat imaging at 4 to 8 weeks to confirm PD	May continue study treatment at the assessment of the investigator and after the participant's consent	Repeat imaging at 4 to 8 weeks to confirm PD per investigator's discretion only.	Discontinue treatment
First radiologic evidence of PD by RECIST 1.1.	Repeat imaging at 4 to 8 weeks to confirm PD.	May continue study intervention at the investigator's discretion while awaiting confirmatory tumor imaging by site by iRECIST.	Repeat imaging at 4 to 8 weeks to confirm PD per investigator's discretion only.	Discontinue treatment
Repeat tumor imaging confirms PD (iCPD) by iRECIST per investigator assessment.	No additional imaging required.	Discontinue treatment (exception is possible upon consultation with Sponsor).	No additional imaging required.	Not applicable
Repeat tumor imaging shows iUPD by iRECIST per investigator assessment.	Repeat imaging at 4 to 8 weeks to confirm PD. May occur at next regularly scheduled imaging visit.	Continue study intervention at the investigator's discretion.	Repeat imaging at 4 to 8 weeks to confirm PD per investigator's discretion only.	Discontinue treatment
Repeat tumor imaging shows iSD, iPR, or iCR by iRECIST per investigator assessment.	Continue regularly scheduled imaging assessments.	Continue study intervention at the investigator's discretion.	Continue regularly scheduled imaging assessments.	May restart study intervention if condition has improved and/or clinically stable per investigator's discretion. Next tumor imaging should occur according to the regular imaging schedule.
iCPD=iRECIST confirmed progressive disease; iCR=iRECIST complete response; iRECIST=modified Response Evaluation Criteria in Solid Tumors 1.1 for immune-based therapeutics; iSD=iRECIST stable disease; iUPD=iRECIST unconfirmed progressive disease; PD=progressive disease; RECIST 1.1=Response Evaluation Criteria in Solid Tumors 1.1; VOP=verification of progression				

Figure 2 Imaging and Treatment for Clinically Stable Participants Treated With Pembrolizumab After First Radiologic Evidence of PD Assessed by the Investigator

iRECIST=modified Response Evaluation Criteria in Solid Tumors 1.1 for immune-based therapeutics; PD=progressive disease; RECIST 1.1=Response Evaluation Criteria in Solid Tumors 1.1.

8.2.2 Eastern Cooperative Oncology Group Performance Scale

The investigator or qualified designee will assess ECOG status at screening, prior to the administration of each dose of study intervention, and during the follow-up period as specified in the SoA (Section 1.3).

8.3 Safety Assessments

Details regarding specific safety procedures/assessments to be performed in this study are provided. The total amount of blood/tissue to be drawn/collected over the course of the study (from prestudy to poststudy visits), including approximate blood/tissue volumes drawn/collected by visit and by sample type per participant, can be found in the Procedures Manual.

Planned time points for all safety assessments are provided in the SoA.

8.3.1 Physical Examinations

8.3.1.1 Full Physical Examination

The investigator or qualified designee will perform a complete physical examination during the Screening period. Clinically significant abnormal findings should be recorded as medical history. The time points for full physical exams are described in Section 1.3. After the first dose of study intervention, new clinically significant abnormal findings should be recorded as AEs.

Investigators should pay special attention to clinical signs related to previous serious illnesses.

8.3.1.2 Directed Physical Examination

For cycles that do not require a full physical examination as defined in Section 1.3, the investigator or qualified designee will perform a directed physical examination as clinically indicated prior to study intervention administration. New clinically significant abnormal findings should be recorded as AEs.

Investigators should pay special attention to clinical signs related to previous serious illnesses.

8.3.2 Vital Signs

The investigator or qualified designee will take vital signs at screening, prior to the administration of each dose of study intervention and during the follow-up period as specified in the SoA. Vital signs include temperature, pulse, respiratory rate, weight, and blood pressure. Height will be measured at screening only. Weight will be measured at screening, at every other cycle, and in follow-up as specified in the SoA.

8.3.3 Electrocardiograms

A standard 12-lead electrocardiogram (ECG) will be performed using local standard procedures. The timing of ECGs is specified in the SoA. Clinically significant abnormal findings should be recorded as medical history. Additional ECGs may be performed as clinically necessary.

8.3.4 Clinical Safety Laboratory Assessments

- Refer to Appendix 2 for the list of clinical laboratory tests to be performed and to the SoA for the timing and frequency.
- The investigator or medically qualified designee (consistent with local requirements) must review the laboratory report, document this review, and record any clinically relevant changes occurring during the study in the AE section of the case report form (CRF). The laboratory reports must be filed with the source documents. Clinically

significant abnormal laboratory findings are those which are not associated with the underlying disease, unless judged by the investigator to be more severe than expected for the participant's condition.

- All protocol-required laboratory assessments, as defined in Appendix 2, must be conducted in accordance with the Laboratory Manual and the SoA.
- If laboratory values from nonprotocol-specified laboratory assessments performed at the institution's local laboratory require a change in study participant management or are considered clinically significant by the investigator (eg, SAE or AE or dose modification), then the results must be recorded in the appropriate CRF (eg, SLAB).
- For any laboratory tests with values considered clinically significantly abnormal during participation in the study or within 30 days after the last dose of study intervention, every attempt should be made to perform repeat assessments until the values return to normal or baseline or if a new baseline is established as determined by the investigator.

Details regarding specific laboratory procedures/assessments to be performed in this study are provided below. The total amount of blood/tissue to be drawn/collected over the course of the study (from prestudy to poststudy visits), including approximate blood/tissue volumes drawn/collected by visit and by sample type per participant can be found in the Study Procedures Manual. Refer to the Study Flow Chart (Section 1.3) for the timing of laboratory assessments.

8.3.4.1 Laboratory Safety Evaluations (Hematology, Chemistry, and Urinalysis)

Laboratory tests for hematology, chemistry, and urinalysis are specified in Appendix 2.

8.3.4.2 Pregnancy Test

All women who are being considered for participation in the study, and who are not surgically sterilized or postmenopausal, must be tested for pregnancy within 72 hours of the first dose of study intervention. If a urine test is positive or not evaluable, a serum test will be required. Participants must be excluded/discontinued from the study in the event of a positive test result. Repeated pregnancy test (such as monthly testing) may be conducted if required by local regulation.

8.4 Adverse Events (AEs), Serious Adverse Events (SAEs), and Other Reportable Safety Events

The definitions of an AE or SAE, as well as the method of recording, evaluating, and assessing causality of AE and SAE and the procedures for completing and transmitting AE, SAE, and other reportable safety event reports can be found in Appendix 3.

Progression of the cancer under study is not considered an AE as described in Section 8.4.6 and Appendix 3.

Adverse events, SAEs, and other reportable safety events will be reported by the participant (or, when appropriate, by a caregiver, surrogate, or the participant's legally authorized representative).

The investigator and any designees are responsible for detecting, documenting, and reporting events that meet the definition of an AE or SAE as well as other reportable safety events. Investigators need to document if an SAE was associated with a medication error, misuse, or abuse. Investigators remain responsible for following up AEs, SAEs, and other reportable safety events for outcome according to Section 8.4.3.

The investigator, who is a qualified physician, will assess events that meet the definition of an AE or SAE as well as other reportable safety events with respect to seriousness, intensity/toxicity and causality.

8.4.1 Time Period and Frequency for Collecting AE, SAE, and Other Reportable Safety Event Information

- All AEs, SAEs, and other reportable safety events that occur after the participant provides documented informed consent but before intervention randomization must be reported by the investigator if the participant is receiving placebo run-in or other run-in treatment, if the event cause the participant to be excluded from the study, or is the result of a protocol-specified intervention, including but not limited to washout or discontinuation of usual therapy, diet, or a procedure.
- All AEs from the time of intervention randomization through 30 days following cessation of study intervention must be reported by the investigator.
- All AEs meeting serious criteria, from the time of intervention randomization through 90 days following cessation of study intervention or 30 days following cessation of study intervention if the participant initiates new anticancer therapy, whichever is earlier, must be reported by the investigator.
- All pregnancies and exposure during breastfeeding, from the time of intervention randomization through 120 days following cessation of study intervention, or 30 days following cessation of study intervention if the participant initiates new anticancer therapy must be reported by the investigator.
- Additionally, any SAE brought to the attention of an investigator at any time outside of the time period specified above must be reported immediately to the Sponsor if the event is considered related to study intervention.

Investigators are not obligated to actively seek AEs or SAEs or other reportable safety events in former study participants. However, if the investigator learns of any SAE, including a death, at any time after a participant has been discharged from the study, and he/she considers the event to be reasonably related to the study intervention or study participation, the investigator must promptly notify the Sponsor.

All initial and follow-up AEs, SAEs, and other reportable safety events will be recorded and reported to the Sponsor or designee within the time frames as indicated in [Table 12](#).

Table 12 Reporting Time Periods and Time Frames for Adverse Events and Other Reportable Safety Events

Type of Event	Reporting Time Period: Consent to Randomization/ Allocation	Reporting Time Period: Randomization/ Allocation through Protocol- specified Follow- up Period	Reporting Time Period: After the Protocol- specified Follow-up Period	Time Frame to Report Event and Follow-up Information to Sponsor:
Nonserious Adverse Event (NSAE)	Report if: - due to protocol-specified intervention - causes exclusion - participant is receiving placebo run-in or other run-in treatment	Report all	Not required	Per data entry guidelines
Serious Adverse Event (SAE) including Cancer and Overdose	Report if: - due to protocol-specified intervention - causes exclusion - participant is receiving placebo run-in or other run-in treatment	Report all	Report if: - drug/vaccine related. (Follow ongoing to outcome)	Within 24 hours of learning of event
Pregnancy/ Lactation Exposure	Report if: - due to intervention - causes exclusion	Report all	Previously reported – Follow to completion/termination; report outcome	Within 24 hours of learning of event
Event of Clinical Interest (require regulatory reporting)	Report if: - due to intervention - causes exclusion	Report - potential drug-induced liver injury (DILI) - require regulatory reporting	Not required	Within 24 hours of learning of event
Event of Clinical Interest (do not require regulatory reporting)	Report if: - due to intervention - causes exclusion	Report - non-DILI ECIs and those not requiring regulatory reporting	Not required	Within 5 calendar days of learning of event

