5.3.4 Contraception

Pembrolizumab may have adverse effects on a fetus in utero. Refer to Appendix 5 for approved methods of contraception.

Participants should be informed that taking the study medication may involve unknown risks to the fetus (unborn baby) if pregnancy were to occur during the study. In order to participate in the study, participants of childbearing potential must adhere to the contraception requirement (Appendix 5) from the day of study medication initiation (or 14 days prior to the initiation of study medication for oral contraception) throughout the study period up to 120 days after the last dose of study medication. If there is any question that a participant of childbearing potential will not reliably comply with the requirements for contraception, that participant should not be entered into the study.

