6.6.2 Immune-Related Events and Dose Modification (Withhold, Treat, Discontinue)

Dose Modification and Toxicity Management for Immune-related AEs Associated with Pembrolizumab

AEs associated with pembrolizumab exposure may represent an immune-related response. These irAEs may occur shortly after the first dose or several months after the last dose of pembrolizumab treatment and may affect more than one body system simultaneously. Therefore, early recognition and initiation of treatment is critical to reduce complications. Based on existing clinical study data, most irAEs were reversible and could be managed with interruptions of pembrolizumab, administration of corticosteroids and/or other supportive care. For suspected irAEs, ensure adequate evaluation to confirm etiology or exclude other causes. Additional procedures or tests such as bronchoscopy, endoscopy, skin biopsy may be included as part of the evaluation.

Dose Modification and Toxicity Management Guidelines for irAEs associated with pembrolizumab monotherapy, coformulations, or IO combinations are provided in [Table 9](#).

Table 9 Dose Modification and Toxicity Management Guidelines for Immune-related Adverse Events Associated with Pembrolizumab Monotherapy, Coformulations or IO Combinations

General instructions: 1. Severe and life-threatening irAEs should be treated with IV corticosteroids followed by oral steroids. Other immunosuppressive treatment should begin if the irAEs are not controlled by corticosteroids. 2. Pembrolizumab monotherapy, coformulations or IO combinations must be permanently discontinued if the irAE does not resolve or the corticosteroid dose is not ≤ 10 mg/day within 12 weeks of the last treatment. 3. The corticosteroid taper should begin when the irAE is \leq Grade 1 and continue at least 4 weeks. 4. If pembrolizumab monotherapy, coformulations or IO combinations have been withheld, treatment may resume after the irAE decreased to \leq Grade 1 after corticosteroid taper.				
irAEs	Toxicity Grade (CTCAE v5.0)	Action With Pembrolizumab Monotherapy, Coformulations or IO Combinations	Corticosteroid and/or Other Therapies	Monitoring and Follow-up

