8.10.4.3 Survival Follow-up Contacts

Participant survival follow-up status will be assessed approximately every 12 weeks to assess for survival status until death, withdrawal of consent, or the end of the study including early study closure, whichever occurs first.

The first survival follow-up assessment should be scheduled as described below:

- For participants who discontinue treatment intervention and who will not enter the Efficacy Follow-up Phase, the first survival follow-up contact will be scheduled 12 weeks after the discontinuation visit and/or safety follow-up visit (whichever is last).
- For participants who completed assessments in the Efficacy Follow-up Phase, the first survival follow-up contact will be scheduled 12 weeks after the last efficacy assessment follow-up visit has been performed.

Due to early study discontinuation, participants may be enrolled in a pembrolizumab extension study, if available, to continue pembrolizumab monotherapy. The Survival Follow-up contact will not be required for such participants.

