Appendix 2 Clinical Laboratory Tests

This language replaces what is documented in corresponding table footnote.

Footnote to the table reads:

- a. Perform on women of childbearing potential only 72 hours prior to Day 1 of Cycle 1. Pregnancy tests must be repeated approximately monthly.

Norway

Sections 1.3.5 (Table 1)- Schedule of Activities for the End of Treatment and Posttreatment Follow-up Periods

This language replaces what is documented in the corresponding section of the referenced tables.

Assessment	Notes
Pregnancy Test for WOCBP – Urine or Serum hCG	For WOCBP, perform as required locally. If a urine pregnancy test cannot be confirmed as negative, a serum pregnancy test is required. Monthly pregnancy testing should be conducted up to 120 days after the last administration of pembrolizumab.

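### Section 8.4.1 ends SAE reporting at day 30 for anyone who starts new anticancer therapy, whatever the date of that start, and the pregnancy bullet carries the same undated cut

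*Combined protocol and SAP*

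**What the plan says.** Section 8.4.1 sets three post-treatment windows, all starting at randomization.

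- All AEs: "All AEs from the time of intervention randomization through 30 days following cessation of study intervention must be reported by the investigator". New therapy does not change this.
- SAEs: until "90 days following cessation of study intervention or 30 days following cessation of study intervention if the participant initiates new anticancer therapy, whichever is earlier".
- Pregnancy and breastfeeding exposure: until "120 days following cessation of study intervention, or 30 days following cessation of study intervention if the participant initiates new anticancer therapy must be reported".

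The next bullet and Table 12 keep one route open after the SAE window closes: an SAE that reaches the investigator at any time must still be reported if it is considered related to study intervention. Table 12 has no such route for a new pregnancy; after the follow-up period only pregnancies already reported are followed. Inside the windows, SAEs and pregnancies are due within 24 hours of the site learning of them.

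Two other places bear on pregnancy. Section 8.4.5 makes any spontaneously reported pregnancy during the study reportable, with no exception for new therapy. Section 5.3.4 requires contraception "throughout the study period up to 120 days after the last dose of study medication", also with no exception. In Appendix 7, for Norway only: "Monthly pregnancy testing should be conducted up to 120 days after the last administration of pembrolizumab".

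Section 9.6.2 and Table 15 compare the proportion with any serious AE between arms, with 95% confidence intervals. They do not say which post-treatment days count.

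**The concern.** A rule that shortens safety follow-up when another anticancer drug starts would normally use the start date as the cutoff, so that events before the switch still count. Section 8.4.1 does not. It uses the fact of a switch, at whatever date, to set an end point of day 30. An SAE that falls before any other drug is given can therefore be put outside the window by something that happens later. The same SAE in a participant who never switches is inside.

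The comparison of serious AEs between arms is at stake. If arms differ in how many participants switch, they would also differ in how completely days 31 to 90 are captured. For pregnancy, the issue is that the protocol asks for contraception over 120 days but may not require a report of a pregnancy that arises within that period.

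**Working it through.** The plan gives no figure to reproduce, so the check is window arithmetic and a reading of the linked sections.

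**Literal rule.** Let s be the day, counted from cessation, on which new therapy starts. The SAE window ends at day 90 with no new therapy, and at min(90, 30) = 30 with new therapy at any s. Since 30 is below 90 for every s, the closing earlier-of wording does no work. This suggests that the intended cutoff was not written down.

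**Comparison rule.** The window ends at max(30, min(90, s)): it stops at the switch, but not before day 30 or after day 90.

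| New therapy starts | Literal end | Comparison end | Pre-switch days excluded by the literal rule |
|---|---|---|---|
| day 15 | 30 | 30 | 0 |
| day 45 | 30 | 45 | 15 |
| day 60 | 30 | 60 | 30 |
| day 75 | 30 | 75 | 45 |
| day 90 or later | 30 | 90 | 60 |
| never | 90 | 90 | 0 |

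For anyone who ever switches, the literal cut is (90 − 30)/90 = 67% of the SAE window. A switch after day 90 is treated no differently from one on day 60, because the clause has no upper limit on s.

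**Pregnancy.** The literal window for a switcher is 30 of 120 days, so 90 days (75%) are cut. Pre-switch days excluded are 30 for a switch on day 60, 60 for day 90, and 90 for day 120 or later.

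**What this means for a single event.** Take an SAE on day 45 and a switch on day 75.

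- The site learns of it on day 50. No switch has occurred, the 90-day window applies, and the report is due within 24 hours.
- The site learns of it on day 80. The literal window closed on day 30. If the SAE is judged related, it is still reportable; if judged unrelated, it is not required.
- The window is applied to the database at cleaning or analysis. The event is on day 45, the literal end is day 30, and an SAE already reported could be left out of the count. Section 9.6.2 states no counting window, so 8.4.1 is the only one a programmer would find.

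With no switch, the day-45 SAE is reportable and countable in all three situations. Relatedness is judged by investigators who know the assigned arm (6.3.3).

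**The case against.** A reader could say that only a switch within the first 30 days is meant. Section 8.1.7.2 does use such a limit, but there it sets the timing of the Safety Follow-up Visit; 8.4.1 does not contain it. The reading is possible, but it has to be supplied by the reader.

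The stronger objection is that little is lost in practice, and most of this stands. Related SAEs stay reportable without time limit. SAEs learned of before the switch are due within 24 hours, and nothing in the protocol says to delete them. Progression of the melanoma is not reported as an SAE (8.4.6). The Table 15 row is a participant-level proportion, so a dropped SAE matters only if that participant had no other. Section 9.6.2 has no safety hypotheses or Tier 1 events and calls the intervals descriptive.

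Four stronger inferences are tempting, and the documents do not support them.

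- *A sized bias in the serious-AE difference.* This needs post-treatment SAE rates and switching rates by arm, which the documents do not give. Assuming every pre-switch SAE is lost would also ignore the safeguards above.
- *Switching as a consequence of progression.* Section 8.10.4.2 lists new therapy and progression as separate events. A link is plausible but not stated.
- *Loss of late immune-related events.* Section 6.6.2 says "These irAEs may occur shortly after the first dose or several months after the last dose of pembrolizumab treatment", but such events, if attributed to pembrolizumab, are the ones the relatedness route keeps.
- *A late first survival call that should be moved.* Section 8.10.4.3 places that call 12 weeks after the discontinuation or safety visit. However, under Amendment 6 Table 5 has no posttreatment columns, and the contacts end at study closure and are waived for extension-study participants. Rescheduling has no secure footing.

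On pregnancy, 8.4.5 covers spontaneously reported cases during the study, so a 90-day gap is not proven. The contraception and Norwegian testing rules do not themselves govern reporting. What remains is a conflict between two reporting rules.

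**Conclusion.** The drafting fault is real. The SAE clause does not tie its cutoff to the date new therapy starts, and on its literal terms it excludes up to 60 days before the switch. The affected SAEs are those judged unrelated and learned of after the switch, plus any removed if the window is applied to data already collected. The effect on the any-serious-AE comparison is probably small; no percentage-point figure can be given from the documents. A difference between arms would also require that switching differs by arm, which is an assumption.

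The pregnancy bullet has the same undated cut. It contradicts 8.4.5 and leaves reporting up to 90 days shorter than the contraception period. These passages must be reconciled.

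Shortening SAE collection once another anticancer drug has started is a legitimate sponsor choice and is not in dispute. The fault is that pre-switch days are caught by it.

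**What to change.** Make three wording changes.

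1. In the SAE bullet of 8.4.1, let reporting run from randomization to the earlier of 90 days after cessation and the start of new anticancer therapy, but never less than 30 days after cessation. The floor matches the 30-day window for all AEs.
2. In 9.6.2, state that the serious-AE rows of Table 15 count events in that same window.
3. In the pregnancy bullet of 8.4.1, remove the new-therapy cut, so that reporting agrees with 8.4.5 and with the 120 days in 5.3.4.

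The cost is a few more SAE and pregnancy reports and no new visit or call. Because the study is closing early, the second change matters most for data already collected: it settles how they are counted. The rewording still ends SAE collection at the switch when that falls between days 30 and 90, so it restores the days before the switch and not those after it.
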